six patients. If intolerable toxicities arise after three or more cycles in patients otherwise experiencing clinical benefit, patients will have the option of continue pembrolizumab as monotherapy. Special attention will be placed on persistent grade 3 or higher anemia, as myelodysplastic syndromes have been described in around 1.5% of patients receiving olaparib in previous trials[Pujade-Lauraine et al., 2017; Robson et al., 2017; Ledermann et al., 2012; Moore et al., 2014]. Hematologic consultation (with bone marrow aspiration as needed) will be requested for patients developing persistent anemia.

Patients will be followed for three (3) years or until time of death. ORR, PFS, and OS will be determined. Correlative studies will determine the functional status of the Fanconi Anemia pathway promoting homologous recombination repair as well as the microbiome composition in responsive and non-responsive patients. In addition, tumor mutation burden, MSI, and PD-L1 expression will be correlated with Fanconi Anemia pathway status and response to therapy.

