2.2 Trial Schema

2.3 Schedule of Activities

Trial Period:	Screening Phase	Treatment Cycles ^a								End of Treatment	Post-Treatment		
		1	2	3	4	To be repeated beyond 8 cycles					Discon	Safety Follow-up	Follow Up Visits ^b
Treatment Cycle/Title:	Screening					5	6	7	8				
Scheduling Window (Days):	-28 to -1		± 3	± 3	± 3	± 3	± 3	± 3	± 3	At time of Discon ±7	30 days post discon ±7	Every 8 weeks post discon ± 7	Every 12 weeks ±7
Administrative Procedures													
Informed Consent	X												
Inclusion/Exclusion Criteria	X												
Demographics	X												
Medical History	X	X	X	X	X	X	X	X	X				

Trial Period:	Screening Phase	Treatment Cycles ^a								End of Treatment	Post-Treatment			
		1	2	3	4	To be repeated beyond 8 cycles					Safety Follow-up	Follow Up Visits ^b	Survival Follow-Up	
Treatment Cycle/Title:	Screening	1	2	3	4	5	6	7	8	Discon	At time of Discon ±7	30 days post discon ±7	Every 8 weeks post discon ± 7	Every 12 weeks ±7
Scheduling Window (Days):	-28 to -1		± 3	± 3	± 3	± 3	± 3	± 3	± 3					
Prior and Concomitant Medication Review	X	X	X	X	X	X	X	X	X					
Trial Treatment Administration		X	X	X	X	X	X	X	X					
Post-study anticancer therapy status												X	X	
Survival Status												X	X	X
Clinical Procedures/Assessments														
Review Adverse Events			X	X	X	X	X	X	X					
Full Physical Examination	X													
Directed Physical Examination			X	X	X	X	X	X	X					
Vital Signs and Weight	X	X	X	X	X	X	X	X	X					
ECOG Performance Status	X	X	X	X	X	X	X	X	X					
Laboratory Procedures/Assessments: analysis performed by LOCAL laboratory														
Pregnancy Test – Urine or Serum β-HCG	X ^c													
PT/INR and aPTT	X ^a													
CBC with Differential	X ^a	X ^b	X	X	X	X	X	X	X					
Comprehensive Serum Chemistry Panel	X ^a	X ^b	X	X	X	X	X	X	X					
Urinalysis	X ^a													
T3, FT4 and TSH	X ^a				X			X ^f						
Efficacy Measurements														
Tumor Imaging	X				X					X ^d	X			
Tumor Biopsies/Archival Tissue Collection/Correlative Studies Blood														
Archival or Newly Obtained Tissue Collection	X ^e													
Correlative Studies Stool Collection	X ^e				X ^e					X ^e				

^a Must be performed within 10 days of the first treatment visit (Cycle 1 Day 1).

^b Hematology (CBC with differential) and Creatinine results must be available and reviewed by the Investigator prior to infusion. A spot creatinine result may be used to proceed with treatment, as Chemistry results may not be available.

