^c Must be performed within 72 hours of the first treatment visit (Cycle 1 Day 1).

^d Tumor imaging to be done every 9 weeks (within 1 week before every 4th cycle) and will only be required every 12 weeks for patients that have been on treatment for more than 1 year.

^e See Protocol Laboratory Manual.

^f Beginning with Cycle 9, T3, FT4 and TSH will be performed every 3 cycles/9 weeks.

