3.2 Secondary Objective(s), Hypothesis(es), and Endpoint(s)

(1) **Objective:** To determine PFS and OS, defined as time from treatment initiation to disease progression or death.

Hypothesis: The combination of PD-1 and PARP inhibition will result in a progression-free survival advantage for patients with recurrent cervical carcinoma.

Secondary Endpoint: Progression-free survival (PFS)

(2) **Objective:** To evaluate safety and tolerability per the Common Terminology Criteria for Adverse Events (CTCAEv5.0) [Common Terminology Criteria for Adverse Events https://ctep.cancer.gov/protocoldevelopment/electronic_applications/docs/CTCAE_v5_Quick_Reference_8.5x11.pdf. Accessed September 30, 2018].

Hypothesis: Combination of PD-1 and PARP inhibitors is tolerable in patients with recurrent cervical cancer.

Secondary Endpoint: Toxicities associated with the regimen

(3) **Objective:** To evaluate if baseline tumor deficiencies in the Fanconi Anemia pathway are associated with antitumor responses to the combination as assessed by the FATS1 assay, performed on archived paraffin embedded tumor tissues.

Hypothesis: Deficiencies in homologous recombination (HR) repair based on the Fanconi Anemia Triple Stain Immunofluorescence (FATS1) assay will predict a higher iORR to the combination of pembrolizumab and olaparib in patients with cervical cancer.

Secondary Endpoint: Immune overall response rate (iORR)

(4) **Objective:** To determine duration of response (DoR).

Hypothesis: The combination of PD-1 and PARP inhibition will result in a duration of response (DoR), defined as time from documentation of tumor response to disease progression, in this cohort.

Secondary Endpoint: Duration of response (DoR)

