6.1.3 Laboratory Procedures/Assessments

Details regarding specific laboratory procedures/assessments to be performed in this trial are provided below.

Laboratory tests for hematology, chemistry, urinalysis, and others are specified in Table 9.

Table 9 Laboratory Tests

Hematology	Chemistry	Urinalysis	Other
Hematocrit	Albumin	Blood	Serum β -human chorionic gonadotropin†
Hemoglobin	Alkaline phosphatase	Glucose	(β -hCG)†
Platelet count	Alanine aminotransferase (ALT)	Protein	PT (INR)
WBC (total and differential)	Aspartate aminotransferase (AST)	Specific gravity	aPTT
Red Blood Cell Count	Lactate dehydrogenase (LDH)	Microscopic exam (If abnormal)	Total triiodothyronine (T3)
Absolute Neutrophil Count	Carbon Dioxide ‡	results are noted	Free tyroxine (T4)
Absolute Lymphocyte Count	(CO_2 or bicarbonate)	Urine pregnancy test †	Thyroid stimulating hormone (TSH)
	Uric Acid		PK
	Calcium		
	Chloride		Stools for correlative studies
	Glucose		
	Phosphorus		
	Potassium		
	Sodium		
	Magnesium		
	Total Bilirubin		
	Direct Bilirubin (If total bilirubin is elevated above the upper limit of normal)		
	Total protein		
	Blood Urea Nitrogen		

† Perform on women of childbearing potential only. If urine pregnancy results cannot be confirmed as negative, a serum pregnancy test will be required.

‡ If considered standard of care in your region.

Table 10 Laboratory safety variables

Haematology/Haemostasis (whole blood)	Clinical Chemistry (serum or plasma)
B-Hemoglobin (Hb)	S/P-Creatinine
B-Leukocyte count	S/P-Bilirubin, total
B-Absolute neutrophil count	S/P-Alkaline phosphatase (ALP)
B-Absolute lymphocyte count	S/P-Aspartate transaminase (AST)
B-Platelet count	S/P-Alanine transaminase (ALT)
B-Mean cell volume (MCV)	S/P-Albumin
	S/P-Potassium
	S/P-Calcium, total
	S/P-Sodium
Urinalysis (dipstick)	S/P-Urea or Blood Urea Nitrogen (BUN)
U-Hb/Erythrocytes/Blood	S/P-Total Protein
U-Protein/Albumin	
U-Glucose	

NB. In case a patient shows an AST **or** ALT $\geq 3 \times \text{ULN}$ together with total bilirubin $\geq 2 \times \text{ULN}$ please refer to Appendix E ‘Actions required in cases of increases in liver biochemistry and evaluation of Hy’s Law’, for further instructions.

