Safety analyses: Safety analyses will be presented descriptively. The focus of adverse event (AE) summarization will be on treatment-emergent adverse event (TEAEs). A TEAE is defined as an AE that occurs or worsens in the period extending from the first dose of study drug to 30 days after the last dose of study drug in this study. TEAEs will be summarized and summary tables will be created to show the number of patients reporting TEAEs by severity grade and corresponding percentages. A patient who reports multiple TEAEs within the same Preferred Term (or System Organ Class) is counted only once for that Preferred Term (or System Organ Class) using the worst severity grade. Separate summaries will be prepared for TEAEs classified as severe or life threatening (Grade 3 or higher); study drug-related AEs; AEs leading to treatment interruption, modification, or discontinuation; serious AEs; and death. Dose interruptions, reductions, and relative dose intensity will also be summarized.

All results including efficacy, PFS, OS and safety analysis will also be reported based on race/ethnicity stratification.

FATSI analysis will be conducted in batches. We expect that similar to mismatch repair deficient patients, the immune-related objective response will be at or above 40% in patients with functional FA deficiency (FATSI negative), and less than 10% in patients without either homologous recombination repair

deficiency or mismatch repair deficiency. Based on our prior screening data, we anticipate that close to 30% of patients will be FA functionally deficient.

Total enrollment of 48 patients is planned. We will report the 90% confidence interval estimates of iORR both overall and by FATSI status using the exact method (Clopper Pearson). However, the planned study is small for a well powered comparison given that we expect only 15 FATSI-negative patients. Instead, variation in iORR by FATSI status will be assessed by considering the one-sided 95% lower confidence limit (95%LCL) for the difference. As an example, an observed increase in iORR for FATSI- patients of 30.9%, based on 6 out of 15 FATSI- responders compared with 3 out of 33 FATSI+ responders, provides 95% confidence that the true increase for patients with FA deficient tumors is at least 7.1%, suggesting that further study of pembrolizumab/olaparib in FA deficient cervical cancer patients is warranted.

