If any of the events above occur, the overall response for that visit is iUPD, and the iUPD evaluation process (see Assessment at the Confirmatory Imaging above) is repeated. Progression must be confirmed before iCPD can occur.

The decision process is identical to the iUPD confirmation process for the initial PD, except in one respect. If new lesions occurred at a prior instance of iUPD, and at the confirmatory scan the burden of new lesions has increased from its smallest value (for new target lesions, their sum of diameters is ≥ 5 mm increased from its nadir), then iUPD cannot resolve to iSD or iPR. It will remain iUPD until either a decrease in the new lesion burden allows resolution to iSD or iPR, or until a confirmatory factor causes iCPD.

Additional details about iRECIST are provided in the iRECIST publication [Seymour et al., 2017].

Appendix 5: Adverse Events: Definitions and Procedures for Recording, Evaluating, Follow-up, and Reporting**14.1.1 Definition of AE****AE definition**

- An AE is any untoward medical occurrence in a clinical study participant, temporally associated with the use of study intervention, whether or not considered related to the study intervention.
- NOTE: An AE can therefore be any unfavorable and unintended sign (including an abnormal laboratory finding), symptom, or disease (new or exacerbated) temporally associated with the use of a study intervention.
- NOTE: For purposes of AE definition, study intervention (also referred to as Merck product) includes any pharmaceutical product, biological product, vaccine, diagnostic agent, or protocol specified procedure whether investigational or marketed (including placebo, active comparator product, or run-in intervention), manufactured by, licensed by, provided by, or distributed by Merck for human use in this study.

Events meeting the AE definition

- Any abnormal laboratory test results (hematology, clinical chemistry, or urinalysis) or other safety assessments (e.g., ECG, radiological scans, vital signs measurements), including those that worsen from baseline, considered clinically significant in the medical and scientific judgment of the investigator.
- Exacerbation of a chronic or intermittent pre-existing condition including either an increase in frequency and/or intensity of the condition.
- New conditions detected or diagnosed after study intervention administration even though it may have been present before the start of the study.

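### Laboratory values collected throughout treatment have no planned analysis, so laboratory toxicity rates rest on what investigators choose to report and may be understated, chiefly for lower-grade abnormalities

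*Combined protocol and SAP*

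**What the plan says.** Safety and tolerability under CTCAE v5.0 is the second secondary objective (section 3.2): "Secondary Endpoint: Toxicities associated with the regimen".

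Laboratory data are collected repeatedly. Section 6.1.3 says: "Laboratory tests for hematology, chemistry, urinalysis, and others are specified in Table 9". The Schedule of Activities (2.3) marks the blood count and chemistry panel at screening and at every cycle, repeated beyond cycle 8, and a footnote adds: "Hematology (CBC with differential) and Creatinine results must be available and reviewed by the Investigator prior to infusion". Thyroid tests are done at screening and at intervals on treatment, with the footnote: "Beginning with Cycle 9, T3, FT4 and TSH will be performed every 3 cycles/9 weeks".

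The safety paragraph of section 7.2 works from reported events: "The focus of adverse event (AE) summarization will be on treatment-emergent adverse event (TEAEs"). It continues: "TEAEs will be summarized and summary tables will be created to show the number of patients reporting TEAEs by severity grade and corresponding percentages". It adds separate summaries for grade 3 or higher, drug-related and serious events, events leading to a treatment change, and deaths, plus dose interruptions, reductions and relative dose intensity. Nothing in section 7.2 summarizes a laboratory value.

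Appendix 5 (14.1.1) decides when a laboratory result becomes an event. Its list of qualifying events includes abnormal hematology, chemistry or urinalysis results "considered clinically significant in the medical and scientific judgment of the investigator".

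**The concern.** Several harms that the protocol anticipates are defined by laboratory measurements: anemia, other cytopenias, liver enzyme and bilirubin rises, and thyroid dysfunction. Section 2.0 singles one out because of myelodysplastic syndrome: "Special attention will be placed on persistent grade 3 or higher anemia". For such harms the measured value is the most direct evidence of grade, and the trial will hold it for every cycle.

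The planned tables use instead the subset of abnormalities that an investigator chose to report. The trial is open-label and multi-center, and the rule sets no grade threshold, so two sites could treat the same asymptomatic value differently. An abnormality that is not recorded can only lower the reported rate, which makes the regimen look more tolerable. Section 7.2 also uses treatment-related toxicity as an outcome in the microbiome prediction models, so incomplete recording could carry over into those models.

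**Working it through.** The SAP states no figure on this point, so there is none to reproduce. The check is a comparison of the texts.

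**Is any laboratory analysis planned?** Section 7.2 contains no worst grade derived from values, no shift table, no change from baseline and no count of patients meeting the liver criteria of section 6.2.6.

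**Must a graded value be recorded as an event?**
- The list in Appendix 5 (14.1.1) depends on judged clinical significance.
- A note in the same definition allows that an abnormal laboratory finding can be an event and omits that qualifier. It does not require every graded value to be recorded.
- Section 12.1(d) requires the investigator to evaluate and comment on out-of-range values. It does not make them events.

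**Where would an unrecorded abnormality still leave a trace?**

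| Abnormality | What the protocol requires | Room for under-recording |
|---|---|---|
| Hb below 8 g/dl (Table 12) | Olaparib interruption; reason entered in eCRF (6.2.1.2) | Small |
| Grade 3-4 neutropenia, leukopenia, thrombocytopenia (Table 13) | Same | Small |
| AST/ALT with bilirubin rise (6.2.6) | Reported to the supplier on numeric criteria | Small, but section 7.2 does not list it for summary |
| Grade 1-2 neutropenia, leukopenia, thrombocytopenia (Table 13) | Continuing is left to judgement | Present |
| First grade 2 anemia (Table 12) | Continuing is left to judgement | Present |
| Grade 2-4 hypothyroidism, grade 2 hyperthyroidism (Table 4) | Pembrolizumab continues | Present; no dose change need follow |

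**How large could the effect be?** The documents give no recording rate. If n of 48 patients have a given graded abnormality and each is recorded independently with probability c, the expected reported rate is n × c / 48, and the chance that at least one is missed is 1 − cⁿ. Only the 48 comes from section 7.2; n and c are assumed, to show the arithmetic for lower-grade abnormalities.

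| n (true rate) | c = 80% | c = 90% | c = 95% | c = 100% |
|---|---|---|---|---|
| 20 (41.7%): reported rate | 33.3% | 37.5% | 39.6% | 41.7% |
| 20: chance of at least one missed | 98.8% | 87.8% | 64.2% | 0% |
| 5 (10.4%): reported rate | 8.3% | 9.4% | 9.9% | 10.4% |
| 5: chance of at least one missed | 67.2% | 41.0% | 22.6% | 0% |

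Non-recording moves the rate down or leaves it unchanged.

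**The case against.** The strongest reply is that the serious events are already protected. Severe cytopenias force an interruption whose reason goes into the eCRF, and section 7.2 summarizes grade 3 or higher events, events leading to interruption, and interruptions themselves. For such an event to vanish, an investigator would have to stop the drug for it, record why, and still judge it not clinically significant. This stands: a reader might infer a substantial loss of grade 3-4 cytopenias, and the documents do not support that. Even so, an interruption summary does not give rates by analyte and grade.

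A reader might also infer that event tables cannot separate anemia present at entry from worsening on treatment, since Table 1 admits hemoglobin of 9.0 g/dL and Table 12 places that in grade 2. That inference fails. Section 7.2 counts events that begin or worsen after the first dose, so stable entry anemia is excluded and a fall to grade 3 is included. What a worst-grade table omits is the starting grade, which a shift table supplies.

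Third, laboratory toxicity is not wholly unexamined: the first six patients are assessed over two cycles for grade 4 hematologic and grade 3 or higher non-hematologic toxicity (section 2.0). That is correct, but the assessment serves a dose decision for later patients and gives no rate for the trial.

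Finally, safety analysis is descriptive and the primary decision rule is untouched. That limits the weight of the point without removing it.

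**Conclusion.** The omission is real. Section 7.2 bases toxicity rates on reported events, the specific rule for laboratory results turns on investigator judgement without a CTCAE threshold, and the blood counts, chemistry and thyroid tests collected on treatment have no planned analysis. Rates may be understated and may vary by site, chiefly for lower-grade or asymptomatic abnormalities and for analytes with no mandated action.

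A reader might go further and say that the rates will be understated. The documents do not establish that: if every graded abnormality is recorded, nothing is lost. Nor is the net error in the tables certain to be downward, because investigators also assign the grade (Appendix 5, 14.1.4) and grading errors can run either way. The size cannot be derived from the documents. This is an inexpensive improvement to the evidence for a secondary objective and has no bearing on the primary conclusion.

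**What to change.** Add the following descriptive tables to section 7.2, reported alongside the treatment-emergent event tables:

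- For hemoglobin, neutrophils, platelets, lymphocytes, AST, ALT, bilirubin and creatinine: worst on-treatment CTCAE v5.0 grade derived from the laboratory values, baseline-to-worst shift, and number and percent reaching grade 3-4.
- Number of patients meeting the combined AST/ALT, bilirubin and alkaline phosphatase criteria of section 6.2.6.
- Number of patients with TSH or FT4 outside the normal range after a normal baseline.

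State the on-treatment window and the denominator; the window already used for treatment-emergent events would serve.

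The cost is SAP wording and programming. Testing is done at local laboratories, and section 12.1(d) lets values and reference ranges be attached to the CRF instead of entered on it, so some data entry may be needed. Reported laboratory toxicity may look slightly less favourable. No dose, clinical rule, sample size or primary decision rule changes.

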4.1.3 The Interplay between DNA repair deficiency and Immune Checkpoint inhibition

Le et al. reported a Phase II study evaluating the clinical activity of pembrolizumab, in 41 patients with progressive metastatic carcinoma with or without mismatch-repair deficiency [Le et al., 2015]. The immune-related objective response rate and immune-related progression-free survival rate were 40% (4 of 10 patients) and 78% (7 of 9 patients), respectively, for mismatch repair-deficient colorectal cancers and 0% (0 of 18 patients) and 11% (2 of 18 patients) for mismatch repair-proficient colorectal cancers. The median progression-free survival and overall survival were not reached in the cohort with mismatch repair-deficient colorectal cancer but were 2.2 and 5.0 months, respectively, in the cohort with mismatch repair-proficient colorectal cancer.

Interestingly, patients with mismatch repair-deficient non-colorectal cancer had responses similar to those of patients with mismatch repair-deficient colorectal cancer (immune-related objective response rate, 71% [5 of 7 patients]; immune-related progression-free survival rate, 67% [4 of 6 patients]). Whole-exome sequencing revealed a mean of 1782 somatic mutations per tumor in mismatch repair-deficient tumors, as compared with 73 in mismatch repair-proficient tumors ($P=0.007$), and high somatic mutation loads were associated with prolonged progression-free survival ($P=0.02$). Since somatic mutations have the potential to encode "non-self" immunogenic antigens the authors hypothesized that tumors with a large number of somatic mutations due to mismatch-repair defects may be susceptible to immune checkpoint blockade.

Vergote et al. is evaluating the combination of pembrolizumab to traditional carboplatin and paclitaxel followed by olaparib maintainence therapy, KEYLYNK-001, as first line treatment in BRCA-nonmutated patients with advanced epithelial ovarian cancer [Vergote et al., 2019]. Similarly, KEYLYNK-009 is evaluating efficacy of olaparib plus pembrolizumab with chemotherapy plus

pembrolizumab after induction with first-line chemotherapy plus pembrolizumab in triple negative breast cancer (TNBC). The primary hypotheses are that olaparib plus pembrolizumab prolongs progression-free survival (PFS) compared with chemotherapy plus pembrolizumab.

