7.0 STATISTICAL ANALYSIS PLAN

7.1 Statistical Analysis Plan Summary

7.2 Statistical Analysis Plan

Sample size calculation: Single-Stage design will be used for this study [A'Hern, 2001; Fleming, 1982]. The study will require 48 subjects to decide whether the proportion responding (P), is less than or equal to 0.130 or greater than or equal to 0.280. If the number of responses is 10 or more, the hypothesis that $P \leq 0.130$ is rejected with a target error rate of 0.100 and an actual error rate of 0.087. If the number of responses is nine or less, the hypothesis that $P \geq 0.280$ is rejected with a target error rate of 0.100 and an actual error rate of 0.099.

Efficacy analyses: The iORR will be defined as the proportion of patients with an “immune” complete response (iCR) or “immune” partial response (iPR). For the primary iORR analysis in all the treated population, patients with an iCR or iPR will be counted as successes and all other patients (including those with missing response information) will be counted as failures. The percentage of iORR with its 95% confidence interval (CI) will be presented.

Progression free survival (PFS) will be defined among all treated patients as the time from first dose of study drug until the first date of either disease progression or death due to any cause. The date of disease progression will be defined as the earliest date of disease progression based on central review. For patients whose disease has not progressed at the time of the analysis, censoring will be performed using the date of the last valid disease assessment. The data will be analyzed by the Kaplan-Meier method. The median PFS time and 95% CI will be recorded.

Overall survival (OS): Median OS will be defined as the time from the beginning of study drug treatment until death due to any cause. For patients who have not died at the time of the analysis, censoring will be performed using the date the patient was last known to be alive. The data will be analyzed by the Kaplan-Meier method. The median OS and 95% CI will be recorded.

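### Do the FATSI response expectations in Section 7.2 undercut the 90% power stated for the primary rule?

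*Combined protocol and SAP*

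**What the plan says.** The sample size paragraph of Section 7.2 sets up an exact single-stage design. With 48 patients, the trial decides whether the overall response proportion "is less than or equal to 0.130 or greater than or equal to 0.280". Ten or more responses reject the lower value, with an actual error rate of 0.087. The other branch begins "If the number of responses is nine or less" and rejects the upper value, with an actual error rate of 0.099.

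The FATSI paragraphs of the same section expect iORR to be "at or above 40% in patients with functional FA deficiency (FATSI negative), and less than 10% in patients without either" homologous recombination or mismatch repair deficiency. On prevalence they say "we anticipate that close to 30% of patients will be FA functionally deficient", which they take as 15 patients. They concede that the trial is too small for a well-powered comparison by FATSI status and plan a one-sided 95% lower confidence limit for the difference instead. The illustration is a difference of 30.9 percentage points, "based on 6 out of 15 FATSI- responders compared with 3 out of 33 FATSI+ responders". From it the section concludes only that more study in FA-deficient patients would be justified.

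Section 3.2 lists the FATSI question as a secondary objective. Section 4.1.3 gives the mismatch-repair-deficient response rates on which the 40% appears to be modelled: 4 of 10 in colorectal and 5 of 7 in non-colorectal tumours.

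**The concern.** Two parts of one section appear to describe different trials. The first implies 90% power. The second gives subgroup expectations whose weighted average, at the figures quoted, is about 19%, far nearer the 13% null than the 28% alternative. If 19% were the investigators' real expectation, the primary rule would be met in fewer than half of such trials, and the 0.099 would give a misleading picture of the trial's prospects.

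The worked example sharpens the doubt. It is the only hypothetical result in the SAP and is presented as encouraging, yet its 9 responses fall on the failing side of the primary rule, which the text does not mention. The stakes would be an overstated chance of success, and a subgroup finding used to soften a negative primary result.

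**Working it through.** **Inputs (Section 7.2 unless noted).** N = 48; success at 10 or more responses; p0 = 0.13; p1 = 0.28; FATSI-negative share about 30%, taken as 15 of 48, leaving 33; expected iORR at least 0.40 in FATSI-negative patients and below 0.10 in patients with neither deficiency. Section 4.1.3: 4/10 and 5/7.

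**1. The plan's own figures.** For X ~ Bin(48, p):

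- P(X ≥ 10 | 0.13) = 0.0865 (stated 0.087).
- P(X ≤ 9 | 0.28) = 0.0995 (stated 0.099), so power is 0.9005.

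Both reproduce apart from the last digit of the second. Among sample sizes from 30 to 59, N = 48 with a cut-off of 10 is the smallest design with both errors at or below 0.10.

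**2. Overall rate if the limits are taken as point values and 10% is applied to everyone who is not FATSI-negative.**

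- 30% share: 0.30 × 0.40 + 0.70 × 0.10 = 0.190.
- 15/33 split: (15 × 0.40 + 33 × 0.10)/48 = 9.3/48 = 0.194.
- 14/34 split (since 48 × 0.30 = 14.4): (5.6 + 3.4)/48 = 0.1875.

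**3. Chance of 10 or more responses in those cases.** Bin(48, 0.19) gives 0.430. The exact sum of Bin(15, 0.40) and Bin(33, 0.10) gives 0.457. The 14/34 version gives 0.410. The range is 41% to 46%.

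**4. Do the expectations exclude 28%?** With the remainder at 10%, an overall 28% requires (0.28 × 48 − 3.3)/15 = 0.676 in FATSI-negative patients, or (0.28 − 0.07)/0.30 = 0.70 with the 30% share. Both satisfy a statement of 40% or more, and both lie just below 5/7 = 0.71.

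**5. How far the answer moves within or near the stated limits (15/33 split).**

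| FATSI-negative | Others | Overall | P(≥ 10) |
|---|---|---|---|
| 40% | 5% | 15.9% | 0.20 |
| 40% | 10% | 19.4% | 0.46 |
| 50% | 10% | 22.5% | 0.69 |
| 60% | 10% | 25.6% | 0.86 |
| 71% | 10% | 29.1% | 0.97 |

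The 10% ceiling does not cover FATSI-positive patients who are mismatch-repair deficient. The documents give no share for them. Assuming 3 of the 33, responding at 40%, the overall rate is (6 + 1.2 + 3.0)/48 = 21.3% and P(≥ 10) is 0.59.

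**6. The example.** 6 + 3 = 9 and 9/48 = 18.75%. P(X ≥ 9 | 0.13) = 0.164, so the null is not rejected, and the primary rule rejects 28% or more. The example's difference is 6/15 − 3/33 = 0.400 − 0.091 = 0.309, which is the quantity it is meant to illustrate.

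**The case for a change.** The strongest case for a change is that the subgroup figures are the plan's only stated view of how responses will be distributed, and that the example treats them as central values: 40% in FATSI-negative and 9.1% in all 33 FATSI-positive patients. On that reading the trial is close to a coin-flip. The caveat about limited size concerns only the FATSI comparison, not the primary rule. Nor is the example's pattern rare. If the true rates were 40% and 10%, a FATSI difference with a lower limit above zero together with 9 or fewer responses would occur in about 35% of trials (Wald limit) to 40% (Newcombe limit). A sentence or two would forestall argument over how to read it.

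The arithmetic stands, and so does the observation that Section 7.2 never links 28% to the FATSI expectations. The inference that something is wrong does not. Reaching 41% to 46% takes three choices that the text does not make: the floor for one group, the ceiling for the other, and no mismatch-repair-deficient patients among the FATSI-positive. A true rate near 19% lies between the two values the design separates, where intermediate power is expected. The 0.099 is already attached in the text to 28% or more, so nothing is concealed. The reading of 9 responses is also fixed in advance: the primary rule has no exception for a FATSI signal, and the FATSI analysis is secondary.

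**Conclusion.** No change is needed. The design delivers the error rates it states. The subgroup expectations are bounds that permit an overall rate of 28% and do not contradict it, and the example illustrates a secondary confidence limit without claiming that the trial would succeed. A negative primary result alongside a signal in FA-deficient patients is a coherent outcome, and proposing further study in that group is a proportionate response to it.

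What remains is missing explanation. At 40% and 10%, the overall iORR is about 19% and the chance of meeting the primary rule 41% to 46%. That is a reference value resting on the assumptions in step 2 of the working, not the plan's expected power; across the scenarios shown, the chance runs from 0.20 to 0.97. A statistician applying the plan as written would count 9 responses as a failure and report the FATSI difference as secondary. Sample size, cut-off, endpoint, analyses and conclusions would be the same with or without the extra text.
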